APPENDIX 5: RESPONSE ASSESSMENT IN NEURO-ONCOLOGY (RANO)

As discussed in (Wen, 2010).

Measurable disease is defined as bi-dimensionally contrast-enhancing or enhancing lesions with clearly defined margins by magnetic resonance imaging (MRI) scan, with 2 perpendicular diameters of at least 10 mm, visible on two or more axial slices that are preferably, at most, 5 mm apart with 0 mm skip.

Non-measurable disease is defined as either uni-dimensionally measurable lesions, masses with margins not clearly defined, or lesions with maximal perpendicular diameters less than 10 mm.

All measurable and non-measurable lesions must be assessed using the same techniques as at baseline.

Complete response (CR): Requires all of the following:

- complete disappearance of all enhancing measurable and non-measurable disease sustained for at least 4 weeks
- no new lesions
- stable or improved non-enhancing (T2/fluid-attenuated inversion recovery [FLAIR]) lesions
- subjects must be off corticosteroids (or on physiologic replacement doses only)
- stable or improved clinically

Note: Subjects with non-measurable disease only cannot have a CR; the best response possible is SD.

Partial response (PR): Requires all of the following:

- $\geq 50\%$ decrease compared with baseline, in the sum of products of perpendicular diameters of all measurable enhancing lesions sustained for at least 4 weeks
- no progression of non-measurable disease; no new lesions
- stable or improved non-enhancing (T2/FLAIR) lesions on same or lower dose of corticosteroids compared with baseline scan
- corticosteroid dose at the time of the scan evaluation should be no greater than the dose at time of baseline scan
- stable or improved clinically

Note: Subjects with non-measurable disease only cannot have a PR; the best response possible is SD.

Stable disease (SD): Requires all of the following:

- does not qualify for CR, PR, or progression
- stable non-enhancing (T2/FLAIR) lesions on same or lower dose of corticosteroids compared with baseline scan

In the event that the corticosteroid dose was increased for new symptoms and signs without confirmation of disease progression (PD) on neuro-imaging, and subsequent follow-up imaging shows that this increase in corticosteroids was required because of PD, the last scan considered to show SD will be the scan obtained when the corticosteroid dose was equivalent to the baseline dose.

Note: Stable doses of corticosteroids include subjects not on corticosteroids.

Disease progression (PD): PD is defined by any of the following:

- $\geq 25\%$ increase in sum of the products of perpendicular diameters of enhancing lesions compared with the smallest tumor measurement obtained either at baseline (if no decrease) or best response, on stable or increasing doses of corticosteroids
- significant increase in T2/FLAIR non-enhancing lesion on stable or increasing doses of corticosteroids compared with baseline scan or best response after initiation of therapy not caused by co-morbid events (e.g., radiation therapy, demyelination, ischemic injury, infection, seizures, post-operative changes, or other treatment effects)
- any new lesion; clear clinical deterioration not attributable to other causes apart from the tumor (e.g., seizures, medication adverse effects, complications of therapy, cerebrovascular events, infection) or changes in corticosteroid dose
- failure to return for evaluation as a result of death or deteriorating condition
- clear progression of non-measurable disease

Summary of RANO Response Criteria

Criterion	CR	PR	SD	PD
T1 gadolinium-enhancing disease	None	$\geq 50\%$ decrease	$< 50\%$ decrease but $< 25\%$ increase	$\geq 25\%$ increase ^a
T2/FLAIR	Stable or decrease	Stable or decreasing	Stable or decrease	Increase
New Lesion	None	None	None	Present
Corticosteroids	None	Stable or decreasing dose	Stable or Decreasing dose	NA ^b
Clinical Status	Stable or increase	Stable or increase	Stable or increase	Decrease
Requirement for Response	All	All	All	Any

Abbreviations: CR, complete response; FLAIR, fluid-attenuated inversion recovery; NA, not applicable; PD, progressive disease; PR, partial response; RANO, Response Assessment in Neuro-Oncology; SD, stable disease (Wen, 2010).

^{a.} Progression occurs when this criterion is present.

^{b.} Increase in corticosteroids alone will not be taken into account in determining progression in the absence of persistent clinical deterioration.

CCI

17.4.	Vital Signs.....	33
17.5.	ECHO/MUGA	33
18.	REFERENCES.....	33
	APPENDIX 1.PARTIAL	DATES
	CONVENTIONS.....	35

Algorithm for Treatment Emergence of Adverse Events: 35
Algorithm for Prior / Concomitant Medications: 36

List of Abbreviations and Definitions

Abbreviation	Term
AE	adverse event
AESI	adverse event of special interest
ATC	anatomic therapeutic chemical (classification system)
AUC	area under the concentration-time curve
AUC _{D1}	area under the concentration-time curve on Day 1
AUC _{D15}	area under the concentration-time curve on Day 15
AUC _{0-t}	area under the concentration-time curve from time 0 to the last measurable plasma concentration
AUC _{0-∞}	area under the concentration-time curve from time 0 extrapolated to infinity
β-hCG	beta-human chorionic gonadotropin
BID	twice daily
BOR	best overall response
CI	confidence interval
CL/F	oral clearance
C _{max}	maximum plasma concentration
CR	complete response
CSR	Clinical Study Report
CSRC	Clinical Safety Review Committee
CTCAE	Common Terminology Criteria for Adverse Events
DLT	dose-limiting toxicity
DNA	deoxyribonucleic acid
DOR	duration of response
DVT	deep vein thrombosis
EC ₅₀	half maximal effective concentration
ECG	electrocardiogram
eCRF	electronic case report form
EIAED	enzyme inducing anti-epileptic drug
E _{max}	maximum effect
EPZ-6438	Tazemetostat
ES	epithelioid sarcoma
EZH2	enhancer of zeste homolog-2
GOF	Gain of function
HLGT	high-level group term
IDMC	Independent Data Monitoring Committee
IHC	Immunohistochemistry
ITT	Intent-to-Treat
K _a	first-order absorption rate constant
LLN	lower limit of normal
MedDRA	Medical Dictionary for Regulatory Activities
MRI	magnetic resonance imaging
mRNA	messenger ribonucleic acid

Abbreviation	Term
MRT	malignant rhabdoid tumor
MTD	maximum tolerated dose
NCI	National Cancer Institute
ORR	objective response rate
PD	progressive disease
PDy	pharmacodynamic(s)
PFS	progression-free survival
PK	pharmacokinetic(s)
PR	partial response
PT	preferred term
QTcF	Fridericia correction of QT interval for heart rate
RANO	Response Assessment in Neuro-Oncology
RECIST	Response Evaluation Criteria in Solid Tumors
RMC	renal medullary carcinoma
RTK	rhabdoid tumors of the kidney
SAE	serious adverse event
SAP	statistical analysis plan
SD	stable disease or standard deviation
SI	International System of units
SOC	system organ class
$t_{1/2}$	elimination half life
TEAE	treatment-emergent adverse event
T_{max}	time to maximum concentration
ULN	upper limit of normal
Vd/F	oral volume of distribution
WHO	World Health Organization

1. INTRODUCTION

[figure not shown]
This statistical analysis plan (SAP) describes the planned analyses, excluding pharmacokinetics (PK), pharmacodynamics (PDy) and exploratory endpoints, to be included in the Clinical Study Report (CSR) for the phase 1 Protocol EZH-102. This SAP is based on Amendment 8.0 of the protocol, dated 20 February 2020. This SAP must be approved, the data base locked, analysis populations defined, and protocol deviations identified prior to performing the analyses described in this document.

[figure not shown]
Results of the analyses of PK, PDy parameters and exploratory endpoints are presented in separate documents.

2. STUDY OBJECTIVES AND ENDPOINTS

Objective	Endpoint
Primary	

 Dose escalation: To determine the maximum tolerated dose (MTD) or the recommended Phase 2 dose (RP2D) of tazemetostat when administered as an oral suspension twice daily (BID) in pediatric subjects with relapsed/refractory rhabdoid tumors, integrase interactor 1 (INI1) negative tumors or synovial sarcoma 	
 Incidence and severity of treatment-emergent AEs (TEAEs) qualifying as protocol-defined dose-limiting toxicity (DLTs) in Cycle 1. Establishment of the protocol-defined RP2D and/or MTD.

 Dose Expansion: To evaluate the antitumor activity of tazemetostat as assessed by overall response rate (ORR) in pediatric subjects with relapsed/refractory atypical teratoid rhabdoid tumor (ATRT) (Cohort 1), non-ATRT rhabdoid tumors (Cohort 2), INI1-negative tumors (Cohort 3), and tumor types eligible for Cohorts 1 through 3 or synovial sarcoma with SS18-SSX rearrangement (Cohort 4) using disease-appropriate standardized response criteria 	
 ORR: complete response (CR) + partial response (PR) for each cohort
Secondary	

 Dose Escalation: to evaluate the preliminary antitumor activity of tazemetostat as assessed by ORR using disease-appropriate standardized response criteria 	
 ORR: confirmed CR+PR

 • Dose Expansion: to determine the progression-free survival (PFS) and overall survival (OS) at 24 and 56 weeks and overall in pediatric subjects with relapsed/refractory ATRT (Cohort 1), non-ATRT rhabdoid tumors (Cohort 2), INI1-negative tumors (Cohort 3), and tumor types eligible for Cohorts 1 through 3 or synovial sarcoma with SS18-SSX rearrangement (Cohort 4) using disease-appropriate standardized response criteria 	
PFS at 24 and 56 weeks and overall for each cohort
 
OS at 24 and 56 weeks and overall for each cohort

 • All Subjects: To assess the safety and tolerability of tazemetostat administered as an oral suspension BID and tablet three times daily (TID) 	
 • Adverse Events (AEs), clinical laboratory tests, and other safety measures

 • All Subjects: To assess the pharmacokinetic (PK) parameters of tazemetostat after administration as suspension or tablets in pediatric subjects. 	
 • PK parameters: maximum plasma concentration (C_{max}), time to C_{max} (T_{max}), area under the concentration-time curve from time 0 to last measurable concentration [AUC_{0-t}], area under the concentration-time curve from time 0 to 12 hours post-dose [AUC_{0-12}], elimination half-life ($t_{1/2}$), oral clearance (CL/F), oral volume of distribution (Vd/F), first-order absorption rate constant (Ka); if data permit

 • All Subjects: To evaluate the duration of response (DOR) in subjects achieving a complete response (CR) or partial response (PR) according to disease-appropriate standardized response criteria 	
 • DOR

Exploratory

CCI
 

3. STUDY DESIGN

3.1. GENERAL DESCRIPTION

This is a phase 1, multicenter, open-label dose escalation and dose expansion study of tazemetostat in pediatric subjects with select relapsed or refractory INI1- or SMARCA4-negative tumors. Subjects will be screened for eligibility within 14 days of the planned first dose of tazemetostat. A treatment cycle will be 28 days. Treatment with tazemetostat will continue until disease progression, unacceptable toxicity, or withdrawal of consent. Response assessment will be evaluated after 8 weeks of treatment and every 8 weeks thereafter. Subjects may receive tazemetostat for a cumulative maximum of 2 years.

Dose escalation phase

Using a rolling 6 dose-escalation design (**Table 2**) [Skolnik, 2008], approximately 48 subjects will be enrolled into dose cohorts starting at 240 mg/m²/dose administered orally BID for a total of 480 mg/m²/day. Up to six subjects may be concurrently enrolled into the study. Dose escalation will proceed in increments of 25-33% and dose de-escalation will proceed in decrements of 50%. The dose levels and corresponding doses of tazemetostat are given in **Table 1**.

Table 1: Dose Escalation

Dose level	Dose of Tazemetostat
Level 0	120 mg/m ² BID = 240 mg/m ² /day
Level 1 (starting dose)	240 mg/m ² BID (starting dose) = 480 mg/m ² /day
Level 2	300 mg/m ² BID = 600 mg/m ² /day
Level 3	400 mg/m ² BID = 800 mg/m ² /day
Level 4	520 mg/m ² BID = 1040 mg/m ² /day
Level 5	700 mg/m ² BID = 1400 mg/m ² /day
Level 6	900 mg/m ² BID = 1800 mg/m ² /day
Level 7	1200 mg/m ² BID = 2400 mg/m ² /day
Level 8	1600 mg/m ² BID = 3200 mg/m ² /day

BID = twice daily

For dose escalation decisions, a minimum of 22 days of toxicity data (80% of one cycle) must be available for each subject.

Decisions as to whether to enroll a new subject onto the current, next highest, or next lowest dose level will be made based on available data at the time of new subject enrollment and will be made by the Clinical Safety Review Committee (CSRC) (see protocol Section 11). The dose level assigned will be based on the number of subjects currently enrolled in the cohort, the number of DLTs observed, and the number of subjects at risk for developing a DLT (i.e., subjects enrolled, but who were not yet evaluable for toxicity).

Table 2: Rolling 6 Escalation/De-escalation Parameters

Subjects Enrolled	# Subjects with DLT	# Subjects without DLT	# Subjects with Toxicity Data Pending	Decision When Next Subject Enrolled
2	0, 1	Any	Any	Stay
2	2	0	0	De-escalate
3	0	0, 1, 2	3, 2, 1	Stay
3	0	3	0	Escalate
3	1	0, 1, 2	2, 1, 0	Stay
3	≥ 2	Any	Any	De-escalate
4	0	0, 1, 2, 3	4, 3, 2, 1	Stay
4	0	4	0	Escalate
4	1	0, 1, 2, 3	3, 2, 1, 0	Stay
4	≥ 2	Any	Any	De-escalate
5	0	0, 1, 2, 3, 4	5, 4, 3, 2, 1	Stay
5	0	5	0	Escalate
5	1	0, 1, 2, 3, 4	4, 3, 2, 1, 0	Stay
5	≥ 2	Any	Any	De-escalate
6	0	0, 1, 2, 3, 4	6, 5, 4, 3, 2	Suspend
6	0	5, 6	1, 0	Escalate
6	1	0, 1, 2, 3, 4	5, 4, 3, 2, 1	Suspend
6	1	5	0	Escalate
6	≥ 2	Any	Any	De-escalate

DLT = dose limiting toxicity

The MTD will be determined based on the incidence of DLTs in Cycle 1, although toxicities occurring in subsequent cycles will also be reviewed. If serious toxicities are observed at the MTD in later cycles, a reduction of the MTD may be considered.

The Clinical Safety Review Committee (CSRC) convened on 06-Jul. 2017 to review safety and PK from subjects at the 1200 mg/m² dose level. No DLTs were observed at 1200 mg/m² dose level. Although the Rolling 6 statistical design supported the escalation to the next dose level of 1600 mg/m², elevated chloride levels were observed in 3 of 6 evaluable subjects in the 1200 mg/m² dose level, and at previous dose levels as well. As tazemetostat is formulated as a hydrobromide salt, it was considered that the hyperchloremia could be an artifact of elevations in serum bromide. Thus, bromide levels were evaluated in 2 of 5 subjects on active treatment and were found to be elevated, though without any associated clinical signs or symptoms of

neurologic toxicity associated with bromism. CCI

Given the occurrence of the elevated bromide levels, as well as PD data, a decision was made by the CSRC to proceed to the dose expansion phase of the protocol with the putative RP2D determined to be 1200 mg/m² BID dose level with the understanding that bromide levels as well as clinical signs and symptoms of bromide toxicity would be closely monitored in all newly and currently enrolled subjects receiving tazemetostat with guidelines for immediate dose reduction as indicated.

Dose expansion at MTD or RP2D:

Approximately 72 subjects will be enrolled into the dose expansion in the following cohorts:

- Cohort 1 – approximately 20 subjects with ATRT
- Cohort 2 – approximately 20 subjects with malignant rhabdoid tumors (MRT)/rhabdoid tumors of the kidney (RTK)/selected tumors with rhabdoid features
- Cohort 3 – approximately 20 subjects with INI-negative tumors as follows:
 - Epithelioid sarcoma
 - Epithelioid malignant peripheral nerve sheath tumor
 - Extraskelatal myxoid chondrosarcoma
 - Myoepithelial carcinoma
 - Renal medullary carcinoma
 - Chordoma (poorly differentiated or de-differentiated)
 - Other INI1-negative malignant tumors with Sponsor approval
- Cohort 4 – approximately 12 subjects with one of the tumor types defined in Cohorts 1 through 3 or synovial sarcoma with SS18-SSX rearrangement

Subjects enrolled in cohorts 1-3 will receive the RP2D of 1200 mg/m² BID of tazemetostat in oral suspension. Subjects enrolled in cohort 4 will initially receive 800 mg/m² TID (2400 mg/m²/day) of tazemetostat administered as tablets, with the possibility to switch to BID tablet dosing or suspension dosing in subsequent cycles if unable to comply with the TID schedule. Cohort 4 was added to evaluate the administration of the tazemetostat tablet formulation in pediatric subjects who can swallow tablets, which may be more palatable.

Escalation and Expansion

Subjects will discontinue study treatment at the time of disease progression, development of an unacceptable toxicity, withdrawal of consent by subject and/or parent, or after 2 years of cumulative dosing or termination of the study.

Subjects also will undergo medical history assessment, physical examinations (PEs); vital sign measurements; echocardiogram (ECHO); performance status (Lansky/Karnofsky) assessments, blood sample collection for hematology, chemistry, PK, and PD markers; electrocardiograms (ECGs); adverse event (AE) assessments; concomitant medication assessments; and pregnancy testing for females of childbearing potential.

The study duration is approximately 24 months for each subject. The duration of screening for each subject will be approximately 14 days. The subject accrual period is planned for approximately 15 months. The duration of treatment will vary for each subject. Subjects may receive tazemetostat for a cumulative maximum of 2 years. Subjects will be followed for safety for approximately 30 days after the last dose of tazemetostat. For subjects that discontinue dosing, participation will continue for survival follow-up and response for 2 years from first dose of tazemetostat.

The completion of the primary endpoint of the study is expected to occur approximately 6 months after the date the last subject is enrolled to treatment and evaluated for response. The end of study will occur when the last subject discontinues the study treatment and has had the opportunity to complete the safety follow-up visit (30 days after last dose of tazemetostat) or the long-term survival follow-up period (2 years from first dose of tazemetostat), whichever is later. The study may end prior to this if 80% of enrolled subjects are deceased prior to the collection of the last survival follow-up.

Survival follow-up will continue for 2 years for each subject or until 80% of treated subjects have died.

All patients are to discontinue participation on the study after 2 years of cumulative treatment, regardless of whether they came off study due to clinical response or if they reduced dose.

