15. Has known hypersensitivity to any of the components of tazemetostat or other inhibitor(s) of EZH2, or hypersensitivity to Ora-sweet or methylparaben.

**Dosage and
Administration for
Tazemetostat:**

16. Has an uncontrolled intercurrent illness including, but not limited to, uncontrolled infection, or psychiatric illness/social situations that would limit compliance with study requirements.

17. **For female subjects of childbearing potential:** Is pregnant or nursing

For male subjects: Is unwilling to adhere to contraception criteria from time of enrollment in study to at least 3 months after last dose of tazemetostat.

Oral Suspension: Subjects will receive tazemetostat as an oral agent BID.

The starting dose for the dose escalation will be 240 mg/m²/dose given BID for a total daily dose of 480 mg/m²/day. Dose escalation will be performed using a “Rolling 6” design. The starting dose is derived from physiologically based PK modeling of observed PK data in adult subjects.

Dose Expansion: For patients with no CNS involvement, the dose will be 520 mg/m² given BID. For ATRT and tumors with CNS involvement the dose will be 1200 mg/m² given BID.

Tablet Formulation: Subjects in Cohort 4 will receive orally administered tazemetostat tablets 800 mg/m² TID (2400 mg/m²/day) CCI

Treatment may continue, assuming subject and/or parent/guardian and Investigator consent, until disease progression or unacceptable toxicity. Tazemetostat will be administered for a maximum of 2 years.

Criteria for Evaluation:

Primary Endpoints:

Dose Escalation:

- Incidence and severity of treatment-emergent AEs (TEAEs) qualifying as protocol-defined DLTs, and establishment of the protocol-defined RP2D and/or MTD.

Dose Expansion:

- Overall response rate (CR + PR) to tazemetostat in pediatric subjects with relapsed or refractory ATRT (Cohort 1), non-ATRTR rhabdoid tumors (Cohort 2), INI1-negative tumors (Cohort 3), and tumor types eligible for Cohorts 1 through 3 or synovial sarcoma with SS18-SSX rearrangement (Cohort 4) using disease-appropriate standardized response criteria.

Secondary Endpoints:

Dose Escalation:

- Overall response rate (CR+PR) to tazemetostat in pediatric subjects with relapsed or refractory CNS and solid tumors, using disease-appropriate standardized response criteria

Dose Expansion:

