1.6.5 Anticipated Safety Profile

This section summarizes the anticipated safety profile for tazemetostat based on the clinical experience in 90 pediatric subjects treated as of 24 May 2019 in this ongoing study (EZH-102), on nonclinical toxicology studies, and where noted, on 725 adult subjects treated with tazemetostat.

The following treatment-emergent AEs, regardless of causality, have been observed in $\geq 10\%$ of pediatric subjects in study EZH-102: vomiting, nausea, fatigue, diarrhea, and anemia.

The following nonserious adverse reactions to tazemetostat treatment have been observed in $\geq 2\%$ of pediatric subjects in study EZH-102: vomiting, nausea, fatigue, diarrhea, anemia, decreased appetite, constipation, thrombocytopenia, and neutropenia.

Tazemetostat treatment-related SAEs have been reported in 9 (10%) pediatric subjects in study EZH-102. The only serious adverse reaction reported in ≥ 1 pediatric subject has been decreased appetite (2 subjects).

The most common TEAEs that have led to interruption of tazemetostat dosing in pediatric subjects were: platelet count decreased (7%); hydrocephalus (6%); and thrombocytopenia, neutropenia, diarrhea, intestinal obstruction, dyspnea, hypoxia, and pyrexia (each 2%). The most common TEAEs leading to dose reduction in pediatric subjects have been platelet count decreased and thrombocytopenia, reported in 3 (3%) subjects and 2 (2%), respectively.

In addition, as described in Section 10.4, AESIs identified for the tazemetostat development program include: CCI /T-ALL, MDS, AML, and other myeloid malignancies like MPN. Epizyme considers the risk for CCI /T-ALL in tazemetostat clinical trials to be largely concentrated in pediatric patients. Myeloid malignancies have been reported in 5 of the 725 subjects in the adult population treated with tazemetostat. The risk of myeloid neoplasias as a result of EZH2 inhibition is considered uncertain based on available literature and Epizyme clinical data. Measures are in place to exclude potential subjects who may be predisposed to developing a myeloid neoplasia from participation in clinical studies and for early identification and monitoring of subjects who may be developing a myeloid neoplasia.

Further details of clinical study designs, tazemetostat exposure, and treatment-emergent AEs regardless of causality are outlined in the current IB.

Additionally, there are unknown risks of abnormal pregnancy outcomes and drug-drug interactions.

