4 SUBJECT POPULATION

4.1 Number of Subjects

A total of approximately 120 subjects will be enrolled in this study. Up to 48 subjects are estimated to be enrolled during dose escalation (subjects who discontinue in absence of a DLT prior to the completing of the DLT evaluation period may be replaced). Up to 72 subjects are estimated to be enrolled during Dose Expansion. See Section 14.2.1 for sample size assumptions.

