5.3 Dosage and Administration

Tazemetostat must be dispensed or administered only to subjects enrolled in the study and in accordance with the protocol. Standard institutional procedures for administering an oral agent via by mouth will be followed. An adequate supply will be provided with instructions on home administration.

Tazemetostat administered to newly enrolled subjects: Based on benefit-risk assessment of the population studied in this clinical trial, following a report of CCI in a pediatric patient, from the time Amendment 7.0 approval to the completion of enrollment, the following doses will be the starting dose for new enrolled patients: For new patients with ATRT or any INI1-negative tumors with CNS involvement, the starting dose will remain 1200 mg/m² BID. For new patients that are non-ATRT, the starting dose will be 520 mg/m² BID. (See Section 6.5.3).

Tazemetostat administered as an oral suspension: The starting dose of tazemetostat (for dose escalation only) will be 240 mg/m²/dose given BID (based on free base) = 480 mg/m²/day. The amount of suspension per dose is calculated based on the subject's body surface area (BSA) and the assigned dose level. After the completion of Cycle 1, if a subject is unable to continue dosing with the oral suspension formulation due to adherence issues, the Medical Monitor should be contacted to discuss the possibility of switching to tablet dosing options.

Tazemetostat administered as a tablet (subjects in Cohort 4 only; Cohort 4 is closed to enrollment): Tazemetostat will be orally administered at the dose of 800 mg/m² TID (2400 mg/m²/day). Please see CCI for tablet dosing nomogram. This will provide instruction on the number of tablets to be taken based on BSA. After the completion of Cycle 1, if a subject is unable to continue dosing TID with the tablet formulation because of the quantity of tablets or schedule, the Medical Monitor should be contacted to discuss the possibility of switching to BID tablet dosing or BID suspension dosing.

For subjects on the tazemetostat BID oral suspension schedule, doses should be administered as close to 12 hours apart as possible, but there should be no less than 8 hours between doses. For subjects on the TID tablet schedule, doses should be administered as close to 8 hours apart as possible, but there should be no less than 4 hours between doses. Doses may be taken with or without food.

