6.5 Dose Modification

During dose escalation, dose modifications are not allowed during Cycle 1. Any AE that is severe enough (at the discretion of the Investigator and with permission of the Sponsor/Medical Monitor) to warrant a dose reduction during Cycle 1 will be discussed with the Medical Monitor prior to resumption of study treatment.

Subjects who have an interruption in treatment for >14 days may restart treatment with tazemetostat after consultation with the Medical Monitor.

For any case of CCI /T-ALL, MDS/AML, or other myeloid malignancies like MPN, tazemetostat will be discontinued and the patient will be followed until resolution of the event.

No dose modification is required for the following Grade 3 or greater non-hematologic toxicities:

- Transient fatigue or asthenia
- Transient myalgia or arthralgia
- Nausea that resolves to <Grade 2 within 7 days (with or without anti-emetics)
- Vomiting that resolves to <Grade 2 within 48 hours (with or without anti-emetics)
- Diarrhea that resolves to <Grade 2 within 48 hours

For subjects in the dose-escalation portion of the study, refer to Table 4 for a description of dose levels to be used for dose modification. For example, a dose reduction of one dose level for a subject on a dose of 1200 mg/m² BID would be 900 mg/m² BID and that for a subject at a dose of 900 mg/m² BID would be 700 mg/m² BID.

For subjects on the dose expansion portion of the study, refer to Section 5.3 for new patient dosing levels.

- For subjects starting at 1200 mg/m² BID, refer to Table 6, below, for a description of dose level modifications.
- For subjects on the tablet formulation (Cohort 4), refer to CCI for instructions on how to administer tablets for each dose level.

Table 6. Dose Modification/Dose Reduction for Dose Expansion Portion

Starting Dose	1200 mg/m ² BID - OR - discontinue
Dose Level - 1	900 mg/m ² BID - OR - discontinue
Dose Level - 2	700 mg/m ² BID - OR - discontinue
Dose Level - 3	520 mg/m ² BID - OR - discontinue

- For subjects starting at the 520 mg/m² BID dose level in the dose expansion portion, no dose modifications are permitted. For these subjects, dosing may be interrupted for up to 14 days to allow resolution of AEs, and subjects must be discontinued if the AE does not resolve with dose interruption.

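### SAP 3.1 puts every Cohort 1-3 subject on 1200 mg/m² BID, but Cohorts 2 and 3 can also hold 520 mg/m² starters, whom the cohort ORR and expansion adverse event summaries do not separate

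*SAP*

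**What the plan says.** SAP 3.1 gives one dose for the three suspension cohorts: "Subjects enrolled in cohorts 1-3 will receive the RP2D of 1200 mg/m² BID of tazemetostat in oral suspension". The SAP identifies its source in Section 1: "This SAP is based on Amendment 8.0 of the protocol, dated 20 February 2020".

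Protocol 5.3 sets new starting doses that apply "from the time Amendment 7.0 approval to the completion of enrollment". Subjects with ATRT, or with an INI1-negative tumor involving the CNS, stay at 1200 mg/m² BID. For the rest, "For new patients that are non-ATRT, the starting dose will be 520 mg/m² BID". The protocol synopsis (Dosage and Administration) puts the expansion rule in terms of CNS involvement: "For patients with no CNS involvement, the dose will be 520 mg/m² given BID". Protocol 6.5 then gives this group its own rule: "For subjects starting at the 520 mg/m² BID dose level in the dose expansion portion, no dose modifications are permitted". Dosing may be interrupted for up to 14 days, and the subject must stop if the event does not resolve. Subjects starting at 1200 can step down to 900, 700 and 520.

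On reporting, SAP 6.1 groups expansion subjects by cohort. SAP 15.1 reports the primary ORR by cohort and overall. SAP 17.1 reports adverse events by study part and overall. SAP 3.2, which lists departures from the protocol, does not mention starting dose.

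**The concern.** The SAP sentence is correct for Cohort 1 (ATRT) but not for Cohorts 2 and 3. Protocol 1.5.2.2 shows that expansion opened at 1200 mg/m² BID. Those two cohorts can therefore contain 1200 starters (enrolled before Amendment 7.0, or with CNS involvement) and 520 starters (enrolled later, without it).

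The lower dose was adopted on a benefit-risk assessment after a safety report in a pediatric patient (Protocol 5.3). A reader of the clinical study report will want to know what was seen at that dose, both for adverse events and for response within the cohort where the primary endpoint sits. None of the planned summary tables just described shows this. The expansion table of TEAEs leading to dose reduction also counts 520 starters in its denominator, although they have no reduction step.

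**Working it through.** **1. The stated error rates.** Inputs from Protocol 14.2.1 and SAP 4.4: n = 20 per cohort, success at 3 or more responses, null ORR 5%, target ORR 20%.
- P(X ≥ 3 | n = 20, p = 0.05) = 0.0755, stated as 8%.
- P(X ≤ 2 | n = 20, p = 0.20) = 0.2061, stated as 21%; power 0.794.

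Both reproduce.

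**2. Does mixing doses disturb the rule?** Assume a cohort whose average ORR is 20% but whose two dose groups differ. P(X ≥ 3 of 20) is the sum over two independent binomials:
- 10 subjects at 25% and 10 at 15%: 0.796
- 10 at 30% and 10 at 10%: 0.803
- 15 at 25% and 5 at 5%: 0.801
- all 20 at 20%: 0.794

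Mixing alone leaves the rule's performance essentially unchanged.

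**3. What the cohort ORR can hide.** Exact (Clopper-Pearson) 95% intervals, for an assumed 10/10 split:
- whole cohort, 3/20 = 15%: 3.2% to 37.9%
- one dose, 3/10 = 30%: 6.7% to 65.2%
- other dose, 0/10 = 0%: 0% to 30.8%

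The cohort line is the same whichever dose produced the responses. With no 520 starters, nothing is hidden.

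**4. Where the SAP uses *dose level*.**

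| Place | Use | Separates starting doses within Cohort 2 or 3? |
|---|---|---|
| SAP 6.1 and 15.1, ORR | By dose level across both phases | No; pools phases and tumor types |
| SAP 15.1, duration of response | By dose level within and across study parts, and by cohort | Not clearly; responders only |
| SAP 14, exposure | By dose level and cohort within study part | Possibly; not TEAE, SAE or AESI incidence |
| SAP 15.1, primary ORR | By cohort | No |
| SAP 17.1, adverse events | By study part | No |

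The by-cohort adverse event layout in Protocol 14.5.3 would also mix the doses. The term is not defined for expansion subjects, whose dose can change: by the step-downs in Protocol 6.5, by the reduction to 520 that is one option one year after response, and by rechallenge at 520 or 1200 (Protocol 6.5.3). Two programmers could place the same subject at different levels.

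**5. Are the regimens different in exposure?** Protocol Table 2 gives Day 15 geometric mean AUC(0-24) of 29,700 ng·h/mL at 1200 and 12,500 at 520, a ratio of 29,700/12,500 = 2.4. Each rests on 6 subjects, and 700 mg/m² gave only 8,140 (n = 6), so the contrast is imprecise.

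**6. The dose-reduction table.** If a share f of expansion subjects start at 520 and have no reduction step, the printed rate is the rate among the others multiplied by (1 − f). When f = 0 there is no dilution. The documents do not give f.

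**The case against.** The strongest reply is that no planned calculation uses the wrong sentence. The protocol governs dosing, and the compliance formula in SAP 14.2 divides by the assigned dose, so it is not tied to 1200. The same protocol that introduces the second dose keeps the hypothesis and the primary ORR by cohort, and the SAP follows it. On this view the sentence is a documentation slip and the dose split is an optional display. That stands as regards the test. It does not remove the gap in the safety summaries, and the SAP already adds an unplanned within-cohort ORR subgroup, by prior radiotherapy, for descriptive purposes.

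A second reply is that the information is not lost. SAP 17.1 plans by-subject listings of all adverse events, with separate SAE and AESI listings, and SAP 7 says listings are typically sorted by study part and dose level or cohort. Protocol 14.4.2 also mentions cohorts in its dose-level ORR summary, though the wording is ambiguous and the SAP does not carry it over. This stands in part: counts by starting dose could be rebuilt by hand, but no summary table would show them.

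Three stronger readings are tempting and should not be drawn.
- A reader might infer that the primary test or its power is compromised. Steps 1 and 2 show otherwise. A cohort whose true average ORR is below 20% would pass less often, but that is the rule working as intended.
- A reader might infer that SAP 6.1 confines *dose level* to escalation. Its next sentence uses the term across both phases.
- A reader might estimate the number of 520 starters from "90 pediatric subjects treated as of 24 May 2019" and "A total of approximately 120 subjects will be enrolled in this study". Allowing for the 8 unfilled Cohort 4 places, 120 − 8 − 90 = 22. The documents do not date Amendment 7.0, 24 May 2019 is only a data cut, the enrollment targets are approximate, and later subjects with CNS involvement still start at 1200. The 22 is not a count of 520 starters.

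**Conclusion.** The point holds, and should be fixed before database lock. SAP 3.1 contradicts the protocol amendment that it names as its basis. Cohorts 2 and 3 can hold two starting doses with different modification rules, and the by-cohort primary ORR and study-part TEAE, SAE and AESI summaries do not separate them. *Dose level* needs a definition for expansion subjects.

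The contradiction is certain because it is textual. The size of the reporting consequence is unknown: it depends on how many Cohort 2 and 3 subjects start at 520, which could be few or none. The 10/10 split in the working is an assumption used to show the mechanism. No test, threshold, analysis population, compliance formula or error rate needs to change.

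**What to change.** - Correct SAP 3.1 to the two starting doses. From Amendment 7.0: 1200 mg/m² BID for ATRT or CNS involvement, 520 mg/m² BID otherwise.
- Define *dose level* for expansion subjects as assigned starting dose, wherever SAP 6.1, 14 and 15.1 use the term.
- Add starting-dose columns to the expansion TEAE, SAE and AESI summaries, with a footnote that 520 starters have no reduction step.
- Show ORR (n and exact 95% CI) by starting dose within Cohort 2 and within Cohort 3, labeled as descriptive.

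The cost is SAP wording and a few table columns; no new data are needed. The cells will be small: 2/10 would carry an exact 95% CI of 2.5% to 55.6%. Starting dose is confounded with CNS involvement and enrollment period, so the display should carry no test or inference between doses.
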